6.0 LABELING

Sample labeling will follow FDA regulations and the sponsor standard operating procedure. If applicable, the SoftWave device label will include, (in accordance with 801.1):

Statement: "CAUTION--Investigational device. Limited by Federal (or United States) law to investigational use."

Additionally, the label or other labeling will describe all relevant contraindications, hazards, adverse effects, interfering substances or devices, warnings, and precautions.

Directions for use are contained in the SoftWave Instructions for Use

7.0 CONSENT MATERIALS

Forms and informational materials which are provided to the subject during the informed consent process are listed below:

Form/Informational Material Description
Post Treatment Instructions
Informed Consent Form

9.0 OTHER INSTITUTIONS

If a part of the study is conducted by an institution that has not previously been identified within the Investigational plan each institution's contact information will be documented below;

No other institutions will be part of this study.

10.0 ADDITIONAL RECORDS AND REPORTS

If this is an IDE study, additional records and reports will be maintained on the investigation in addition to those prescribed in 21 CFR 812 sub-part G. If this is a non-IDE study, the study summary will be maintained on the investigation and may include those prescribed in 21 CFR 812 sub-part G.

Additional Records and Reports:

Report	Submit To	Description/Constraints
N/A	N/A	This is a non-IDE study; no additional records or reports will be maintained.

11.0 PREGNANCY

Females may not participate in this study if they are pregnant, breastfeeding, were pregnant within the last three months or are planning a pregnancy during the study.

If the subject thinks they have become pregnant during the study, it is important that they inform the Investigator immediately. If she becomes pregnant or thinks that she may be pregnant, she will be removed from the study and will be asked to perform a final evaluation similar to the final follow-up visit. The Investigator may request to track the pregnancy and will report the pregnancy to the Sponsor and IRB.

12.0 SUBJECT WITHDRAWAL

The subject is free to withdraw from this study at any time. The subject must inform the Investigator immediately if they intend to withdraw. To terminate the subject's participation in this study, they must contact the Investigator at the contact information listed on page one of the informed consent form. They will be asked to come to the study clinic or Investigators office to complete a final follow up visit and may be asked to perform end of study procedures. Their decision to participate in this study or to withdraw from this study will not influence the availability of their future medical care and will involve no penalty or loss of benefits to which they are otherwise entitled.

The Investigator in charge of the study can remove the subject from this study without their consent for any reason, including, but not limited to:

- His/her judgment that any condition or circumstance may jeopardize their welfare or the integrity of the study.
- Their failure to follow the instructions of the Investigator(s).
- If the study is stopped by the sponsor and/or Investigators participating in the study prior to completion.

Data collected prior to withdrawal will be used in data analysis but after withdrawal no further data will be collected.

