2.14 Adverse Event Recording

All data captured must be supported by the Investigator's timely assessment and documentation of the adverse event in the case report forms or source documents. All documented adverse events will be reviewed by the Sponsor or designee to determine whether the adverse event meets regulatory reporting requirements and to ensure timely adverse event reporting to meet local and global regulatory requirements. All adverse events must be followed until their resolution.

Adverse Events Pertaining to the SoftWave Device:

Potential adverse effects associated with shock wave treatments include those listed below:

- Transient moderate increase in pain
- Redness and swelling
- Hematoma and petechial hemorrhage
- Headaches and fainting during extracorporeal shock wave treatments
- Short-term hypoesthesia
- Nausea during therapy
- Tingling during therapy

Adverse Events Pertaining to the Marker:

Using a marker has minimal risks and may produce effects on the body such as redness or a rash.

Adverse Events Pertaining to Ultrasound Gel:

The gel is a water-based gel that may be placed on the skin during treatment. No known adverse events are documented. However, an allergic reaction is always possible when placing a topical gel onto the skin. Allergic reaction may include a mild reaction such as skin redness, irritation, or hives.

Biopsies

Complication with biopsies can include pain, redness, swelling, infection, bleeding, scarring and skin texture irregularities.

Lidocaine

You may experience pain and numbness at the site of the injection. You may also experience redness, rash, infection, skin damage or nerve damage at the site of the injection. You may experience temporary loss of sensation and muscle function at the site of injection.

1% lidocaine (Lidocaine) with Epinephrine Injection

Lidocaine with epinephrine contains the preservative sodium metabisulfite which may cause allergic-type reactions including anaphylactic symptoms such as itching, hives, swollen areas of the body, and/or trouble breathing and life-threatening or less severe asthmatic episodes in certain susceptible people.

Other Cautions:

Incomplete response or no response may occur since some subjects may not respond to treatment.

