14.0 ADVERSE REACTIONS DEFINITIONS AND REPORTING REQUIREMENTS

All adverse events that occur, starting from the time of the first treatment, will be recorded in the source documents and Case Report Forms (CRF).

Adverse Events (AE) occurring will be captured and followed until the condition resolves, stabilizes, is otherwise explained, or the subject is lost to follow-up. Subjects will be instructed that they may contact the Investigator at any time throughout the course of the study.

The Investigator and/or designated study staff will review each event and assess its relationship to the study device (not related, unlikely, possible, probable, and highly probable). The following definitions will be used for rating relationship to the SoftWave treatments:

- Not related – The event is clearly related to other factors such as the subject's clinical state, therapeutic interventions, or concomitant medications administered to the subject.
- Unlikely – The event was most likely produced by other factors such as the subject's clinical state, therapeutic interventions, or a concomitant medication administered to the subject; and does not follow a known response pattern to the investigational product.
- Possible – The event follows a reasonable temporal sequence from the time of investigational product administration; **and/or** follows a known response pattern to the study sampling sessions; **but** could have been produced by other factors such as the subject's clinical state, therapeutic interventions, or concomitant medications administered to the subject.
- Probable – The event follows a reasonable temporal sequence from the time of investigational product administration; **and** follows a known response pattern to the investigational product; **and** cannot be reasonably explained by other factors such as the subject's clinical state, therapeutic interventions, or concomitant medications administered to the subject.

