Adverse events, whether serious or non-serious, will be followed until the condition is resolved, stabilized, otherwise explained or the subject is lost to follow-up. Adverse events will be captured throughout the study and where appropriate, medical tests and examinations will be performed to document the resolution of event(s). Outcomes may be classified as resolved, improved, unchanged, worse, fatal, unknown or lost to follow-up. Following the resolution of any study-associated adverse events there will be no further adverse event reports for that subject.

Reporting Adverse Events:

Report	Submit To	Description/Constraints
Adverse Events, Unanticipated Adverse Device Effect	IRB and Sponsor	If an unforeseen complication is determined to be an unanticipated adverse device effect, the investigator's report must be submitted within 10 working days after the investigator first learns of the effect.
Serious Adverse Events	IRB and Sponsor	The sponsor must be notified within 24 hours of serious adverse events. The IRB must be notified within 1 working day of serious adverse events as defined by FDA guidelines.

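### Section 12.0 ends all data collection at withdrawal with no safety exception, which conflicts with the adverse event follow-up in 2.14 and 14.0 and leaves the moment and scope of withdrawal undefined

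*Combined protocol and SAP*

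**What the plan says.** Section 12.0 (Subject Withdrawal) covers two kinds of exit. A subject may withdraw at any time, and in that case "They will be asked to come to the study clinic or Investigators office to complete a final follow up visit", possibly with end-of-study procedures. Separately, "The Investigator in charge of the study can remove the subject from this study without their consent for any reason", with the subject's welfare among the listed examples. The section then ends with its only rule on data: "Data collected prior to withdrawal will be used in data analysis but after withdrawal no further data will be collected".

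Three other sections bear on what happens after exit:

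- Section 2.14 (Adverse Event Recording): "All adverse events must be followed until their resolution".
- Section 14.0 (Adverse Reactions Definitions and Reporting Requirements): "Adverse Events (AE) occurring will be captured and followed until the condition resolves, stabilizes, is otherwise explained, or the subject is lost to follow-up". The same section repeats the four end points for serious and non-serious events alike: "Adverse events, whether serious or non-serious, will be followed until the condition is resolved, stabilized, otherwise explained or the subject is lost to follow-up".
- Section 11.0 (Pregnancy): if a subject becomes pregnant, or thinks she may be, "she will be removed from the study and will be asked to perform a final evaluation similar to the final follow-up visit". It adds: "The Investigator may request to track the pregnancy and will report the pregnancy to the Sponsor and IRB".

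Section 2.15.3 keeps everyone who starts treatment in the analysis, completer or not. It defines the safety set by receipt of at least one treatment and the presence of some safety data. (That definition also refers to randomization, which is a separate matter.)

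**The concern.** Data collection after exit is limited by one section and required by two others. A site holding an open adverse event for a subject who has left must either stop recording, against 2.14 and 14.0, or go on recording, against 12.0. Section 21.0 allows no deviation without sponsor approval outside a medical emergency, so either course departs from the protocol. With two centers, the sites may also settle the question differently.

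What is at stake is safety information on people who leave early. Collecting adverse events is the stated safety objective in 1.2, and an acceptable side effect profile is one of the additional success criteria in 2.15.1. Some who leave may do so because of a reaction, and for them the later course of the event is of particular interest. Subjects whom the investigator removes have not themselves refused data collection, so respect for a withdrawn consent does not explain stopping their safety data.

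**Working it through.** The point rests on the text and the plan has no figure to reproduce, so the check sets the sections side by side.

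**1. An adverse event still open at exit.**

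| Section | Stated end of follow-up | Withdrawal or removal listed? |
|---|---|---|
| 2.14 | Resolution only | No |
| 14.0 (stated twice) | Resolution, stabilization, another explanation, or loss to follow-up | No |
| 12.0 | Withdrawal, for all data | It is the end point |

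A subject who withdraws but can still be reached is not lost to follow-up. For that subject 14.0 continues and 12.0 stops. No section says which prevails. This conflict carries the point on its own.

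**2. The final visit.** Section 12.0 asks for this visit and then bars data after withdrawal. Whether the visit falls before or after the bar depends on when withdrawal takes effect, and the protocol does not define that moment. This is an ambiguity, not a firm contradiction. Resolving it would not help with an event that outlasts the visit.

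**3. Scope of the rule.** The closing sentence of 12.0 speaks of withdrawal, while the text on investigator exits in 12.0 and pregnancy exits in 11.0 speaks of removal.

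- In favour of one rule for all exits: the section heading, and 2.12, which treats subjects who withdrew and those who were withdrawn together.
- Against: the difference in wording.
- If removal is covered, the final evaluation in 11.0 and any pregnancy tracking come after the point at which data stop.
- If removal is not covered, 12.0 gives no data rule for removed subjects.

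**4. Effect on the safety tables.** Section 2.15.6 summarizes outcomes as number and percent of patients, x/n.

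- A treated leaver with some safety data stays in n (2.15.3).
- An event that begins after exit and is not recorded is missing from x. For such events the reported x/n can only be equal to or below the true value.
- For an event already open at exit, x still includes it. What is missing is its later course. Missed worsening makes the profile look better than it is, and a missed recovery leaves the outcome unknown.
- Scale: the planned total is 50 subjects including departures (2.15.2). On the assumption that all 50 are treated, each subject with a wholly unrecorded event lowers the reported percentage by 1/50 = 2 percentage points. The step is larger if fewer than 50 are treated.

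The number of such subjects cannot be derived. The protocol gives no expected withdrawal rate and no expected adverse event rate.

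**5. Effect on the primary objective.** The pain score is taken during treatment (2.7), and the schedule in 2.13 places it at treatment visits only. Data that stop after withdrawal therefore leave it essentially untouched.

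**The case against.** The strongest reply is that 12.0 can be read in sequence. The subject announces an intention to leave, attends an exit visit, and only then does collection stop. On that reading the final visit yields data that 12.0 itself says will be analysed. This stands as a fair reading, and a reader should not infer that the final visit is bound to produce nothing usable. The text does not state the sequence, however, and an event that outlasts the visit is still caught.

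Second, 11.0 is a specific provision, with its own final evaluation and a mandatory report to the sponsor and IRB, and can be read as overriding a general sentence. This also stands. Tracking the pregnancy is something the investigator may request, so it would be wrong to say that 12.0 breaches a duty to track. Which provision governs is nevertheless left unstated.

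Third, a reader might infer that reactions which drive subjects out vanish from the results and that the adverse event profile is therefore biased toward acceptability. The documents do not support that. An event that prompts exit occurred before exit, is recorded under 14.0 and is used under 12.0. Section 14.0 also allows an outcome to be coded as unknown. The criterion in 2.15.1 is a physician's judgment with no numerical threshold, so a changed conclusion cannot be shown. What remains is a possible understatement through new late events and unrecorded worsening.

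Finally, the informed consent form (Attachment IV) was not available for this review and may say what happens after withdrawal. That limits certainty about practice at the sites, but it would not cure the conflict in the protocol.

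**Conclusion.** The conflict between 12.0 and the follow-up duty in 2.14 and 14.0 is real and cannot be read away for an adverse event open at exit in a subject who can still be reached. The moment of withdrawal and the rule's reach over removed subjects are undefined. This is an internal inconsistency that should be fixed. It is not a flaw that undermines the trial.

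Its consequence is confined to safety data. For treated subjects who leave, the later course of open events and any new late events can go unrecorded while the subjects stay in the denominator. This can understate the profile used for an additional success criterion. It holds to the extent that sites apply the closing sentence of 12.0 literally. Events recorded before exit still count, and the primary pain score is essentially unaffected. The total size of the loss cannot be computed from the documents. The only figure available is the step of 2 percentage points per subject with a wholly unrecorded event, which assumes that all 50 are treated.

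**What to change.** Reconcile 12.0 with 11.0, 2.14 and 14.0, using the same wording in each:

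- (a) State when withdrawal takes effect, and that data from the final visit are collected and analysed.
- (b) For subjects who stop treatment or are removed, including for pregnancy, and who have not withdrawn consent to data collection: continue to record open adverse events to the end points in 14.0, and record the outcome of any pregnancy that is tracked. Bring the end point in 2.14 into line with 14.0.
- (c) For subjects who withdraw consent: offer the final visit and safety follow-up, and stop collection only for what they decline.
- (d) Record the type of exit and the reason for it in one CRF field.

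The cost is a protocol amendment with IRB approval, matching consent wording, one CRF field and some extra contact with leavers. No new visit is needed, because 11.0 and 12.0 already ask for one. The change works best if made before subjects leave, since outcomes not collected at the time may not be recoverable.

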13.0 PHOTOGRAPHY

Standardized photographs will be taken of the treatment area. The subject will be asked to remove jewelry, make-up, and lotions prior to each photo session. Photographs will be taken with an appropriate high-resolution digital camera. Camera settings (lighting, distance, background, polarization, etc.) will be reproduced at each visit, so that photographs are suitable for comparison. Photographs will be taken of the treatment area for study purposes. If the subject does not wish to have their photographs taken, they cannot be in the study.

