2.10 Biopsy Portion of the Study

- Subjects may enroll in the biopsy portion of this study. If the subject has signed the biopsy consent form and enrolled, the following will also be performed:
 - Biopsies may be taken from a treated area the day of treatment and/or may be taken 1, 3, 7 (+/- 1 day), 14 (+/- 2 days), 21 (+/- 2 days), and/or 30 days (+/- 3 days) post last treatment. A control will also be taken on the contralateral side of the treatment area.
 - Biopsy subjects may receive up to 6 biopsies.
 - A local anesthetic, such as lidocaine, may be injected to the area prior to biopsy.

- A 2 mm or 3mm punch biopsy (based on Physician assessment) will be taken from the treatment area.
- Sutures may be used to close the incision site.
- The subject may be asked to attend a 1 week (7-14 days) post each biopsy visit to remove the sutures and assess side effects.
- The following post biopsy treatment instructions will be reviewed:
 - Slight redness, initial tenderness to the wound site is normal; however, if you experience more redness, swelling, pain, pus, or drainage contact the study site immediately.
 - If the biopsy site begins to bleed, apply direct pressure for 10-20 minutes. If it continues to bleed, call the study site immediately.
 - Keep the wound dry today and remove bandage in 24 hours and leave off.
 - Avoid hot tubs, pools, and ocean until sutures are removed. Avoid soaking in water until 14 days after your biopsy.
 - When showering, wash carefully and do not scrub or traumatize the treated skin, or allow spray of shower to strike the skin directly. If the skin is treated harshly, this can increase the risk of scarring.
 - After showering, lightly pat dry the wound or let it air dry, then cover the biopsy site with an application of Vaseline (or petroleum jelly) at least 1-2 times daily. Keeping the wound moist reduces infection, minimizes scarring, and prevents crust formation over the wound.
 - Band-Aids (or any generic Adhesive Bandages) may be used for sleeping or in daily routines where the area may be rubbed/irritated. Whenever possible, keep Band-Aid (or generic Adhesive Bandage) off of the area and keep the area moist with Vaseline (or petroleum jelly) as previously described but do not allow drying out and forming a hard scab.

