2.13 Evaluation Methods

Photographs:

Photographs will be taken at all visits and will be used to assess efficacy and safety of treatment.

Treatment Discomfort/Pain Evaluation:

Subjects will be asked to report the general level of treatment discomfort on a scale of 0 (none) to 10 (maximum intolerable pain) using the universal pain assessment tool (Appendix B)

Subject and Clinician Satisfaction Questionnaire:

The subject will be asked their level of satisfaction using a 6-point Likert scale that ranges from “extremely satisfied” to “extremely unsatisfied.”

Subject Satisfaction	
Rating	Description
6	Extremely Satisfied
5	Satisfied
4	Slightly Satisfied
3	Slightly Unsatisfied
2	Dissatisfied
1	Extremely Unsatisfied

Blinded Evaluation:

Three blinded independent reviewers will perform a photographic evaluation in which they will be asked to identify pre-treatment images when compared to post treatment images. The reviewers will be Board Certified Dermatologist and/or Surgeons and be chosen based on availability and have relevant clinical experience. They will attend a training session prior to grading.

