2.15 Statistical Analysis**2.15.1 Hypothesis**

For this study to be considered a success, the average pain score is acceptable to the Physician as it relates to the type of treatment.

For additional objectives to be considered a success, the following criteria must be met:

- The side effect profile (adverse events) is acceptable to the Physician as it relates to the type of treatment.
- The subject satisfaction rates at the follow up visit will be $\geq 80\%$ (optional).
- Correct identification of pre-treatment images when compared to post treatment (30 and/or 90 day) images will be $\geq 80\%$ (optional).
- Successful collection of biopsies (optional).
- Successful collection of treatment assessment questionnaires (optional).

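### The photographic criterion has no untreated-skin reference, so a correct-identification rate of 80% or more cannot be attributed to the device

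*Combined protocol and SAP*

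**What the plan says.** Section 13.0 (Photography) states twice what is photographed: "Standardized photographs will be taken of the treatment area" and "Photographs will be taken of the treatment area for study purposes". It standardizes the camera ("Camera settings (lighting, distance, background, polarization, etc.) will be reproduced at each visit, so that photographs are suitable for comparison") and prepares the subject ("The subject will be asked to remove jewelry, make-up, and lotions prior to each photo session").

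Under 2.13 Evaluation Methods, photographs serve to assess efficacy as well as safety. Three blinded independent reviewers read them, and "they will be asked to identify pre-treatment images when compared to post treatment images". Section 2.15.1 makes the result a success criterion: "Correct identification of pre-treatment images when compared to post treatment (30 and/or 90 day) images will be" at least 80%, marked optional.

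The only untreated reference in the protocol is in the optional biopsy portion (2.10): "A control will also be taken on the contralateral side of the treatment area". Nothing comparable is specified for the images. The study is open label with no untreated arm (2.2), and the optional comparison device (4.0) is itself a shockwave treatment.

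**The concern.** A reviewer who correctly picks the earlier image shows that something visible changed in a recognizable direction. That does not show that treatment changed it. Section 13.0 holds the camera, lighting and surface products constant. It cannot hold the skin constant, and it says nothing about sun exposure, hair or shaving. The post-treatment instructions in 2.5 are also silent on these. The advice on sun protection in 2.10 concerns biopsied skin only.

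Blinding stops reviewers being told the order of the images. It does not stop them inferring the order from a cue unrelated to the device. Because the study is meant to support additional marketing claims (1.1, 2.1), a rate above the threshold is likely to be read as evidence of a device effect. Without an untreated reference there is no estimate of the rate that would occur anyway. One cannot be created afterwards unless untreated skin happens to be in the baseline frame.

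**Working it through.** The 80% threshold has no derivation in the documents, so there is no planned figure to reproduce. Three things can be checked.

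**1. Scheduled gap between baseline and follow-up image**

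Inputs: up to 5 treatments, 3 to 14 days apart (2.7); follow-up at 30 and 90 days after the last treatment (2.9); window of 1 week either side (2.13 Schedule of Visits and Procedures); baseline photograph before the first treatment (2.6).

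- Treatment period: one treatment gives 0 days; five at the widest spacing give 4 × 14 = 56 days.
- 30-day image: 0 + 30 − 7 = 23 days to 56 + 30 + 7 = 93 days.
- 90-day image: 0 + 90 − 7 = 83 days to 56 + 90 + 7 = 153 days, about 5 months.
- The COVID-19 provision in 2.9 allows a final visit within 1 year of the last treatment: up to 56 + 365 = 421 days.

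These run from the first treatment. A photograph taken at an earlier screening visit would lengthen them.

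**2. Identification rate with no device effect**

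Assumptions, none of them in the documents: images are shown as pairs; a share c of pairs carries a visible non-device cue; reviewers read the direction of that cue correctly in a share r of those pairs; all other pairs are guessed at 50%.

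Rate = 0.5 × (1 − c) + c × r

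| c | r = 0.5 | r = 0.6 | r = 1 |
|---|---|---|---|
| 0.1 | 50% | 51% | 55% |
| 0.3 | 50% | 53% | 65% |
| 0.5 | 50% | 55% | 75% |
| 0.6 | 50% | 56% | 80% |

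If direction is misread more often than not (r below 0.5), the rate falls below 50%.

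**3. Chance of meeting the threshold with no device effect**

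Exact binomial, one reading per subject:

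| True rate | At least 40 of 50 | At least 16 of 20 |
|---|---|---|
| 50% | 0.00001 | 0.006 |
| 65% | 0.016 | 0.12 |
| 70% | 0.079 | 0.24 |
| 80% | 0.58 | 0.63 |

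The threshold is therefore a strong guard against guessing. Whether it guards against non-device change depends on c and r, which the plan gives no means of measuring. If untreated skin were read in the same way, a cue affecting both sites equally would give the same expected rate on both and an expected difference of zero, whatever c and r are.

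**The case against.** The strongest objection concerns direction. Reviewers must say which image came first, not merely whether two images differ. Tan, hair or season shows a difference but gives no order unless the reviewer can tell which way it ran. No image dates are mentioned as being given to reviewers, and enrollment is expected to spread over 6 months (1.3), so season at baseline can differ between subjects. This stands. It rules out the stronger reading that a reader might infer, that the criterion is biased towards success or will be met falsely. The documents do not support that: the cue rate is unknown, its direction is unknown, and even at 65% the chance of reaching 40 of 50 is 0.016. An expected 80% without any device effect would need cues correctly read in about 60% of pairs.

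The endpoint is also optional, and the primary objective is pain. Section 2.15.1 does not say in words that identification proves a device effect. Camera standardization, trained blinded reviewers and the bar on other procedures in the treatment area (2.3) all help. Section 13.0 does not forbid surrounding skin in the frame. These points lower the weight of the concern, but none supplies a reference rate.

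A simple untreated comparison could also mislead. Biopsy marks on treated skin could identify the later image, and 2.7 permits test spots close to the treatment area. A rule that the treated rate need only exceed the untreated rate would be met about 46% of the time with no effect (50 readings each, both rates 65%, taken as independent). The fix has to deal with all three.

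**Conclusion.** The concern holds as a limit on interpretation. The plan specifies photographs of the treatment area only, uses them to assess efficacy, and sets an 80% criterion with no untreated reference. Identification therefore cannot be attributed to the device. That conclusion follows from the text and needs no assumption about cue rates.

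The size cannot be fixed from the documents. For an assumed 30% of pairs with a cue, the no-effect rate is anywhere from 50% to 65% when direction is read at least as well as chance, given paired images and guessing otherwise. The gap of up to 153 days applies only to the 90-day image after five treatments at maximum spacing and a late visit; for the 30-day image the maximum is 93 days.

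This should be changed because it is cheap and cannot be relied on to be recoverable later. It does not touch the primary objective.

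**What to change.** - **13.0:** at baseline and at each photographic follow-up, image an untreated area (contralateral or adjacent; not treated with either device, not test-spotted, not biopsied) under the same settings. Where the existing frame already shows such skin, a crop may serve.
- **2.13 Evaluation Methods:** the same three reviewers read treated and untreated pairs in random mixed order, without dates. Any treated or untreated image with visible biopsy or suture marks is cropped to remove them or excluded from the comparison.
- **2.15.1:** keep the 80% rate as a descriptive criterion. Report the treated rate, the untreated rate and their within-subject difference, with a 95% confidence interval that allows for three readers per subject. Attribute identification to the device only if the lower limit is above zero.

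The cost is one extra frame or crop per photographic visit, about twice as many pairs for the same reviewers, and some pairs lost to biopsy marks. No new visits or staff are needed. A device claim becomes harder to meet. As a rough guide, treating 50 treated and 50 untreated readings as independent at two-sided 5%, power is about 0.89 for 50% against 80% and about 0.59 for 60% against 80%. Pairing and three readers will change these figures.
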